5.1.3 Statistical Methods for Observational Objectives

[figure not shown]
5.1.3.1 Observational efficacy endpoints

[figure not shown]
Estimation of efficacy for the observational objectives will be performed as described for the primary objective above, using the number of cases meeting each of the observational endpoint definitions; for each estimate of efficacy, a 95% CI will be calculated by an exact method conditional on the total number of cases in both groups.

5.1.3.2 ILI-associated with events and healthcare utilization

Events and healthcare utilization associated with cases of laboratory-confirmed influenza ILI caused by any viral type / subtype and with any ILI occurring within 30 days after the ILI onset will be presented for each vaccine group with statistics presented on [Table 5.1](#).

5.1.3.3

5.1.3.4 Antibody persistence

For antibody persistence evaluation in the re-vaccination cohort, HAI titers against the 4 strains used in Season 1 will be summarized as described in [Section 5.1.2.2](#) for immune response on HAI individual titer, titer ≥ 10 (1/dil), and ≥ 40 (1/dil) at D0 and 28 days after the last vaccination (D28/D56) of Season 1 and at D0 of Season 3. Seroconversion rate in Season 1 and individual titer ratio of D28/D56 over D0 in Season 1 and of D0 in Season 3 over D0 from Season 1 will be also presented.

5.1.4 Complementary analyses

5.1.4.1 Efficacy

The rVE will be displayed per factors such as by region / country, by sex, and by pre-defined baseline medical history (Yes or No), by breastfeeding (Yes or No) for subjects < 24 months of age and by vaccine formulation if applicable for the following efficacy endpoints:

- Primary endpoint: occurrence of ILI laboratory-confirmed as positive for any viral types / subtypes
- Occurrence of ILI laboratory-confirmed positive for viral strains similar to those contained in the vaccine (note: presented by age group and by season as well)

Similarity assessment and frequency distribution for laboratory-confirmed ILI based on ferret antigen and genetic sequencing will be summarized by vaccine group in the FASE.

5.1.4.2 Immunogenicity

For HAI immunogenicity endpoints as listed below per strain, analyses will be displayed per factors such as by region / country, by age group, by sex, by baseline serostatus (< 10 vs \geq 10 [1/dil]), by previous influenza vaccination history, by vaccine formulation if applicable, and by baseline medical history.

- Individual HAI titer on D0 and 28 days after the last vaccination (D28/D56).
- Seroconversion
- Individual titer ratio: 28 days after the last vaccination (D28/D56) / D0.
- Subjects with titer \geq 10 and \geq 40 (1/dil) on D0 and 28 days after the last vaccination (D28/D56)

5.1.4.3 Safety

Solicited reactions within 7 days, unsolicited AEs within 28 days and SAEs including AESIs within 28 days after each vaccination and any vaccination as well as SAEs including AESI within 180 days from 28 days after the last injection will be presented by age group, by season, by region / country, by sex, by vaccine formulation if applicable, and by pre-defined baseline medical history.

5.2 Analysis Sets

Seven analysis sets will be used: the FASE, the PPASE, the Safety Analysis Set (SafAS), the ESafAS, the FASI, the Per-Protocol Analysis Set for Immunogenicity (PPASI), and the IAS.

5.2.1 Full Analysis Set for Efficacy

The FASE will be used for the analysis of all efficacy objectives and is defined as the subset of randomized subjects who received at least 1 dose of the study vaccine. Subjects will be analyzed as randomized.

5.2.2 Per-Protocol Analysis Set for Efficacy

- The PPASE is a subset of the FASE and will be used for primary and secondary efficacy objectives. The subjects presenting with at least one of the following conditions will be excluded from the PPASE:
 - Subject did not meet all protocol-specified inclusion criteria or met at least one of the protocol-specified exclusion criteria
 - Subject did not complete the vaccination schedule according to their previous vaccination history
 - Subject received a vaccine other than the one that he / she was randomized to receive
 - Preparation and / or administration of vaccine was not done as per-protocol

- For previously unvaccinated subjects, subject did not receive the 2nd injection in the proper time window (28 days to 38 days after first injection)
- Subject received non-study influenza vaccine between the 1st study vaccine and the end of surveillance
- Subject did not have at least one contact point more than 14 days after last vaccination and before the end of the surveillance period
- Any other deviation identified during the study conduct and identified as relevant by the clinical team during data review, eg, indicated as excluding subjects from this analysis set in the manual deviations dataset.

Of note, any cases between dose 1 and dose 2 for subjects receiving 2 doses will not be considered in the PPASE analysis.

In the event of a local or national immunization program with a pandemic influenza vaccine or other vaccine, subjects who receive 1 or more doses of pandemic influenza vaccine or other vaccine at any time during the study will not be withdrawn from the study.

Subjects will be analyzed as treated.

5.2.3 Safety Analysis Set

The SafAS will be used for SAEs / AESIs analyses and is defined as those subjects who have received at least one dose of the study vaccine(s). Of note, subjects in the Sentinel Safety Cohort and the Re-vaccination Cohort will be included in SafAS.

All subjects will be analyzed after each dose according to the vaccine they actually received, and after any dose according to the vaccine received at the 1st dose.

5.2.4 Expanded Safety Analysis Set

The ESafAS will be used for the analysis of solicited and unsolicited AEs. Subjects who received at least 1 dose of the study vaccine in the Sentinel Safety Cohort, all subjects in Season 1, subjects in Season 2 and 3 who are randomized into the ESafAS, and the Re-vaccination Cohort in Season 3 will be included in the ESafAS.

All subjects will have their safety analyzed after each dose according to the vaccine they actually received, and after any dose according to the vaccine received at the first dose.

Safety data recorded for a vaccine received out of the protocol design will be excluded from the analysis (and listed separately).

5.2.5 Full Analysis Set for Immunogenicity

The FASI will be used as the main analysis set for secondary superior immunogenicity objective and is defined as the subjects randomized in the Immunogenicity Subset in Season 1 who received at least one dose of the study vaccine and had one post-vaccination blood sample. Subjects will be analyzed as randomized.

5.2.6 Per-Protocol Analysis Set for Immunogenicity

The PPASI is a subset of the FASI and will be used for secondary superior immunogenicity objective as a sensitivity analysis. The subjects presenting with at least one of the following conditions will be excluded from the PPASI:

- Subject did not meet all protocol-specified inclusion criteria or met at least one of the protocol-specified exclusion criteria
- Subject did not complete the vaccination schedule according to their previous vaccination history
- Subject received a vaccine other than the one that he / she was randomized to receive
- Preparation and / or administration of vaccine was not done as per-protocol
- For previously unvaccinated subjects, subject did not receive the 2nd injection in the proper time window (28 days to 38 days after first injection)
- Subject did not provide post-dose serology samples in the proper time window (28 days to 38 days after last vaccination)
- Subject received concomitant treatment that may affect the immunogenicity¹ or a non-study influenza vaccine prior to the post-vaccination blood sample
- Any other deviation identified during the study conduct and identified as relevant by the clinical team during data review, eg, indicated as excluding subjects from this analysis set in the manual deviations dataset.

In the event of a local or national immunization program with a pandemic influenza vaccine or other vaccine, subjects who receive 1 or more doses of pandemic influenza vaccine or other vaccine at any time during the study will not be withdrawn from the study.

Subjects will be analyzed as treated.

5.2.7 Immunogenicity Analysis Set

The IAS will be used for all descriptive immunogenicity objectives and is defined as the subjects in the main cohort randomized in the Immunogenicity Subset in Seasons 1, 2, and 3 and the subjects in the Re-vaccination Cohort in Season 3 who received at least one dose of the study vaccine and had one post-vaccination blood sample. Subjects will be analyzed as treated.

For analysis of immunogenicity by SN and ELLA methods, the subset of IAS with available results on the considered serological method will be used.

For correlate of protection assessment, subjects who are part of both the IAS and the FASE will be considered.

¹ other vaccines, blood products, immune-suppressors, immune-modulators with immunosuppressive properties, anti-proliferative drugs such as DNA synthesis inhibitors

5.2.8 Other Analysis Set(s)

Randomized subjects

A randomized subject is a subject for whom a vaccine group has been allocated.

Subjects with data in CRF

Subjects with data in CRF are subjects for whom data were recorded at a visit (except screening).

5.2.9 Populations Used in Analyses

The primary and secondary efficacy analyses with hypotheses tests will be performed on the PPASE and all the efficacy analyses will be performed on the FASE. The PPASE will be the main analysis set for the non-inferior efficacy analysis and the FASE will be the main analysis for all the superior efficacy analyses.

The secondary immunogenicity analysis for superiority testing will be performed on the FASI and will be confirmed on the PPASI. The secondary analyses for the immunogenicity descriptive assessment will be performed on the IAS.

The analyses of efficacy endpoints for observational objectives and ILI-associated symptoms / events will be performed on the FASE. Analyses of antibody persistence and re-vaccination response will be performed on a subset of IAS enrolled in Seasons 1 and 3 and with blood samples drawn in both seasons.

In addition to the ones above, other analysis sets will be taken into account in the description of the population (eg, the disposition, the demographic, or baseline characteristics).

5.3 Handling of Missing Data and Outliers

Kaplan-Meier plots of the dropouts across time will be provided by vaccine groups and reason for the drop-out for each season on the randomized subjects to explore the missing frequency and pattern due to early withdrawal.

5.3.1 Efficacy

Subjects who discontinued from the study without developing an ILI will be included number of subjects in each vaccine group (ie, N_{HD} or N_{SD}) for the calculation of rVE and its CI for all efficacy objectives. To assess the impact of missing data due to early withdrawal on number of cases in each vaccine group (ie, C_{HD} and N_{SD}), the tipping point analysis (17) will be performed in the FAS. The considered approach will analyze all possible combinations of missing cases that may occur in both vaccine groups

In addition, for primary endpoint if the attrition rate for PPASE is > 10%, a time-to-event analysis will be conducted to address the possible imbalance in the drop-out rates between vaccine groups. Cox proportional hazards model will be used for the comparison of the hazard rates between the 2 vaccine groups. If the assumption of proportional hazards (based on Schoenfeld residuals) is violated, a stratified Cox model by season and age group will be computed.

5.3.2 Immunogenicity

For the secondary confirmatory immunogenicity objective, the missing immunogenicity data will not be imputed. If the degree of missing immunogenicity data in the FASI is unexpectedly high (more than 10%) on HAI data for at least one strain, a sensitivity analysis with multiple imputation methods will be performed. For each missing value, a set of 5 plausible values will be produced based on their predicted distribution, using D0 titer, previous vaccination history against influenza, site and age (as a continuous variable) as covariates.

Number of available subjects for the descriptive summary of immunogenicity response for each strain will be calculated as number of subjects who are in the IAS with available HAI titers, or as number of a subset of the IAS who are randomized to have SN assay or ELLA with available SN or anti-NA titers respectively at the timepoint indicated. No imputation will be performed.

No test or search for outliers will be performed.

5.3.3 Safety

No search for outliers will be performed. In all subject listings, partial and missing data will be clearly indicated as missing.

5.3.3.1 Immediate

Generally, no replacement will be done unless specified otherwise. For unsolicited systemic AEs, a missing response to the “Immediate” field is assumed to have occurred after the 30-minutes surveillance period and will not be imputed.

5.3.3.2 Causality

By convention, all events reported at the injection site (either solicited or unsolicited) will be considered as related to the administered product and then referred to as reactions. In a same way, all solicited systemic events pre-listed in the CRF are also considered as related to vaccination and will be considered as reactions. Missing relationship to vaccine for unsolicited AEs will be considered at the time of analysis as related.

5.3.3.3 Measurements

Partial missing temperatures and measurements too large to measure will be handled as described in [Section 4.4.1.1.1](#).

5.3.3.4 Intensity

For solicited reactions, missing intensities will be handled as described in [Section 4.4.1.1.1](#). For unsolicited AEs, missing intensities will remain missing and will not be imputed.

5.3.3.5 Start Date and End Date

Missing or partially missing start dates for unsolicited AEs (including SAEs) will remain missing and not be imputed, and the time of onset will be considered as missing. Nevertheless unsolicited AEs with missing time of onset will be included in analyses according to the visit collected.

Missing or partially missing end dates for AEs (solicited reactions and unsolicited AEs) will remain missing and not be imputed.

5.4 Interim / Preliminary Analysis

5.4.1 Early Safety Data Review

An initial safety review is planned when the first 100 subjects are enrolled in a sentinel safety cohort. All 100 participants will receive QIV-HD (in this open-label cohort, no comparator vaccine will be administered). After the sentinel safety cohort has been vaccinated and has provided safety data for D0-D7 post-vaccination, an IDMC will convene and review the safety data. During this review, enrollment will be paused. Following a satisfactory safety review by the IDMC, enrollment of subjects will resume in Season 1 (2021-2022 NH).

The safety data collected will be entered into the CRB and will be summarized and reviewed by the Sponsor in a blinded manner. It is understood that this review is based on preliminary data that have not been subject to validation and database lock. The usual and ongoing process of monitoring safety signals outside of those specified in the protocol-defined early safety data review (ESDR) will continue unchanged. No hypothesis testing will be performed for the ESDR therefore the adjustment for alpha is not necessary.

The following safety parameters will be assessed as part of the ESDR review of the sentinel safety cohort in an unblinded manner by the IDMC. They will be collected during a period of 7 days after the vaccination:

- Immediate reactions
- Solicited injection site and systemic reactions
- Unsolicited AEs
- SAEs (including AESIs)

Enrollment will be paused during the IDMC review, and the data will be examined for the following occurrences:

- An SAE (including AESIs) considered as related to the vaccination by the Investigator and Sponsor
- > 10% of subjects experiencing Grade 3 fever within 7 days after vaccination

If any of the above criteria are met, a decision will be made by the IDMC as to whether enrollment in the study will be allowed to resume.

5.4.2 Safety Review at the End of Season 1

At the completion of the collection of safety data at the end of Season 1, the IDMC will be convened to review the safety data of participants in Season 1. Unblinding will be performed by

an independent statistician for the IDMC. Enrollment will not be paused during this IDMC review. Details of safety analyses will be in a separate interim SAP.

No statistical adjustment for alpha is necessary as no hypotheses will be tested.

5.4.3 Trigger for Planning of Extension to Season 4

The likelihood of achieving the expected [REDACTED] per-protocol lab-confirmed influenza cases for the primary endpoint at the end of the Season 3 will be assessed using the weekly number of reported ILI in the CRB (laboratory positivity for influenza need not have been confirmed yet) available in Season 3. It is assumed that after the peak number in the same season occurs the weekly number of reported ILI is exponentially distributed in a monotonically decreasing manner. An exponential regression curve will be plotted to forecast the weekly number of reported ILI until the end of the surveillance period in Season 3. Then, the predicted number of per-protocol cases for the primary endpoint at the end of Season 3 will be calculated as follows:

- 1) Calculate the total number of future ILI until the end of Season 3 based on weekly number of future ILI as forecast above
- 2) Multiply the positivity factor estimated from Season 1 to obtain the total number of future cases for the primary endpoint where the positivity factor is the number of cases for the primary endpoint divided by the number of ILI (Note: Season 2 data may be considered for a more conservative prediction)
- 3) Multiply the per-protocol factor estimated from the observed cases (ie, the number of per-protocol cases divided by the total number of cases for the primary endpoint)
- 4) Add the number of per-protocol cases already observed in the study

If laboratory results are available during this analysis, then observed cases for the primary endpoint in Season 3 will be used directly for the prediction using exponential regression.

Epidemiological data of influenza occurrence may be taken into count for the prediction of weekly number of reported influenza cases for the remaining season.

If the predicted total number of per-protocol cases for the primary endpoint is no less than [REDACTED] cases, there is still an [REDACTED] power to demonstrate the superior efficacy using the [REDACTED] threshold based on a one-sided alpha of 2.5%. If the predicted number is less than [REDACTED] cases, then the planning of a study extension to Season 4 is triggered. If this were to occur, then the total number of subjects needed to demonstrate superior efficacy based on the [REDACTED] superiority threshold, assuming [REDACTED] rVE of QIV-HD to QIV-SD, will be calculated using the overall attack rate observed in 3 seasons (if needed, the attack rate based on the predicted number of case in Season 3 can be used).

Since this blinded sample size re-estimation is based on the total number of evaluable cases in both vaccine groups without using vaccine assignment, no bias can be introduced and the Type I error is well-controlled at the nominal value.

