During the period from the 1st vaccination (D0) until 30 April of the following year for NH subjects or until 31 October of the same year for SH subjects, the site will arrange for an NP swab to be taken if the subject experiences a new onset of fever concomitantly with one or more of the above mentioned symptoms of protocol-defined ILI (that persists for or reoccurs after a period of at least 12 hours).

The NP swab will be obtained as soon as possible and no later than 7 days (between D0 and D6) from the onset of the ILI.

Reporting of events temporally associated with an ILI

In addition to obtaining an NP swab, the site will collect detailed information about the ILI, as well as information on occurrence of ALRI, otitis media, healthcare utilization events (hospitalizations, emergency room visits, and non-routine office visits [including urgent care visits]) and medication use (eg, antibiotics, antivirals).

In the event that an NP swab cannot be collected, the research site will still obtain the above information. All subjects' parents / guardians reporting a suspected ILI will have a 30 day follow-up telephone call.

Laboratory testing for the confirmation of influenza and determination of similarity to vaccine components

All NP specimens will be submitted for analysis by both culture and PCR, and a positive result on either test will be considered a laboratory-confirmed case of influenza.

Positive cultures or positive PCR samples will undergo additional testing (typing, subtyping, and strain identification, utilizing genetic sequencing) to determine if the virus detected is similar to any of those contained in the vaccine formulation for the respective season.

Blood sampling

A subset of randomly selected subjects (the Immunogenicity Subset) will provide 2 blood samples (5mL each):

- Previously vaccinated subjects will provide a pre-vaccination (baseline) blood sample at Visit (V) 01 (D0) and a post-vaccination blood sample at V02 (D28 [+7 days]) for HAI testing and potential SN and enzyme-linked lectin assay (ELLA) testing.
- Previously unvaccinated subjects will provide a pre-vaccination (baseline) blood sample at V01 (D0) and a post-vaccination blood sample at V03 (28 days after V02 [+7 days]) for HAI testing and potential SN and ELLA testing.

Note: the Re-vaccination Cohort will automatically be part of the Immunogenicity Subset

Collection of safety data

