4.4.3 Efficacy

For each subject, the efficacy endpoints will be derived based on a combination of the following items:

ILI occurrence: at each ILI visit, the occurrence of a temperature of $\geq 100.4^{\circ}\text{F}$ (38°C), starting more than 14 days after the 1st vaccination for the Full Analysis Set for Efficacy (FASE) as defined in [Section 5.2.1](#) and last vaccination for the Per-Protocol Analysis Set for Efficacy (PPASE) as defined in [Section 5.2.2](#) and concurrent with at least one other symptom meeting the definition of an ILI¹ will be considered as an ILI occurrence.

Notes:

- The start date of the ILI is the start of fever $\geq 100.4^{\circ}\text{F}$ (38°C)
- Start and end dates of fever are considered as the start and end date of the ILI (when the end date is unknown, the last date the fever is known to be present is used)
- The date of start / end of each symptom is used in comparison of start and end of fever $\geq 100.4^{\circ}\text{F}$ (38°C) to define concurrent symptoms with ILI: when start and end dates for fever and one other protocol-defined symptom are not missing, the start date for fever is \leq the end date for the symptom and the end date for fever is \geq the start date for the symptom

¹ Cough, wheezing, difficulty breathing, nasal congestion, rhinorrhea, pharyngitis (sore throat), otitis, vomiting, diarrhea, shivering, fatigue, headache or myalgia

- After the end of an ILI episode, an interval of 2 days has to pass before a new ILI episode can be considered
- For the primary and secondary objectives, in case of more than one occurrence of the same efficacy endpoint for the same subject, only the first occurrence based on the start date of the fever ($\geq 100.4^{\circ}\text{F}$ [38°C]) is considered for the estimation of vaccine efficacy for the prevention of this endpoint

Modified CDC-defined ILI is the occurrence of a temperature of $\geq 100.4^{\circ}\text{F}$ (38°C), starting more than 14 days after the first vaccination and concurrent with cough or pharyngitis (sore throat). The same derivation rules for ILI occurrence will be used.

PCR-confirmed influenza case: An ILI occurrence is PCR-confirmed as positive for influenza A or B types if the PCR result of the corresponding NP swab, recorded at the corresponding ILI visit in the database and taken within 10 days after the start of the ILI, is positive for influenza.

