Culture-confirmed influenza case: An ILI occurrence is culture-confirmed as positive for influenza A or B types if the virology result of the corresponding NP swab, recorded at the corresponding ILI visit in the database and taken within 10 days after the start of the ILI, is positive for influenza.

Laboratory-confirmed influenza case: An ILI occurrence is laboratory-confirmed as positive for influenza A or B types if it is either PCR- or culture-confirmed (see above).

Strain: Virus strains used for sequencing and vaccine formulations for similarity assessment will be detailed in a separate Appendix to this Statistical Analysis Plan (SAP) when it is available and can be updated up to the database lock.

Genetic similarity: Genetic similarity is defined when a laboratory-confirmed isolate is deemed similar to one of the viral strains contained in the vaccine formulations according to sequencing of full HA gene segments proteins. A strain is considered similar to one of the vaccine strains included in the formulation of the considered season if the sequence of full HA gene matches $\geq 99\%$ with a strain known to be and pre-defined as vaccine-similar. This will be defined in a separate Appendix to this SAP when it is available and can be updated up to the database lock.

Antigenic similarity: Antigenic similarity is defined when a laboratory-confirmed isolate is deemed similar to one of the viral strains contained in the vaccine formulations according to Ferret Antigenicity testing (HAI against a panel of known standard ferret reference antisera).

Similarity to vaccine components: For prevention of laboratory-confirmed influenza illness caused by viral strains similar to those contained in the vaccine in subjects 6 months through 35 months of age, laboratory-confirmed isolate is deemed similar to one of the vaccine components based on antigenic similarity only. For all the other endpoints, similarity is based on antigenic similarity when available or based on genetic similarity otherwise.

Potentially, the same swab can be linked to several ILIs, and several swabs may be taken for the same ILI. Therefore, occurrences of positive swabs attached to an ILI are not necessarily equal to occurrences of ILIs with positive swab.

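### The Season 3 case forecast in SAP 5.4.3 has no term for ILIs that are reported but still awaiting a laboratory result

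*SAP*

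**What the plan says.** Protocol 12.4 leaves the method for predicting the number of evaluable cases to the SAP, and SAP 5.4.3 supplies it. The raw material is the "weekly number of reported ILI in the CRB (laboratory positivity for influenza need not have been confirmed yet". An exponential curve is fitted after the peak, and four steps follow:

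1. Forecast ILIs only: "Calculate the total number of future ILI until the end of Season 3 based on weekly number of future ILI as forecast above".
2. Scale that total to cases by the Season 1 positivity, defined as cases divided by ILIs. Data from Season 2 may be brought in to make the prediction more conservative.
3. Multiply by the per-protocol share among observed cases.
4. "Add the number of per-protocol cases already observed in the study".

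Where results are already in hand, "observed cases for the primary endpoint in Season 3 will be used directly for the prediction using exponential regression".

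SAP 4.4.3 defines a case: "An ILI occurrence is laboratory-confirmed as positive for influenza A or B types if it is either PCR- or culture-confirmed". On timing, SAP 3.2 has the swab taken "no later than 7 days (between D0 and D6) from the onset of the ILI", and SAP 4.4.3 accepts a result from a swab "recorded at the corresponding ILI visit in the database and taken within 10 days after the start of the ILI". Neither document states the time from swab to result. Protocol 7.3.2 leaves the details of swab shipment to the Operating Guidelines.

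The predicted count has two set uses and one optional one. It triggers planning of Season 4 (SAP 5.4.3). It is one of two conditions for the efficacy interim (SAP 5.4.4). If needed, it may also feed the attack rate used to size Season 4 (SAP 5.4.3).

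**The concern.** At any data cut a Season 3 ILI is in one of three states: resulted, reported but pending, or not yet occurred. Steps 1 to 3 convert only the third group, and step 4 adds only confirmed cases from the first. The pending group helps to fit the curve but enters no term of the sum. This is more than missing detail, because the four steps taken literally give a total that leaves out real cases. The section itself expects unconfirmed ILIs, and the four-step route is the one meant for when results are not yet in.

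A forecast that is too low could start Season 4 planning, or run the efficacy interim, when neither was needed. It could also enlarge Season 4 if the predicted count supplies the attack rate.

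**Working it through.** **No figure to reproduce.** The case target, trigger threshold, attack rate and effect size are redacted, and no worked forecast is given. What can be checked is the accounting, and then its size under assumed inputs.

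**Accounting.** Let C be the confirmed per-protocol cases, P the pending ILIs, F the future ILIs, p the positivity factor and g the per-protocol factor.

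- SAP 5.4.3: C + F × p × g
- Full count: C + (P + F) × p × g
- Omitted: P × p × g, which is never negative

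**Size under the SAP's own assumptions.** These are exponential decline and one constant, correct positivity factor. Weekly ILIs are then proportional to weekly cases, the fitted curve is exact, p and g cancel, and forecast/truth = 1 − (cases in pending weeks)/(all Season 3 cases).

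Assumed inputs, none from the documents: 28-week season, peak at week 12, rise 0.35 per week, decline 0.30 per week, cut 3 to 5 weeks after the peak.

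- Relative weekly cases, weeks 12 to 17: 1.0000, 0.7408, 0.5488, 0.4066, 0.3012, 0.2231.
- Season total: 3.3355 (weeks 1-12) + 2.8348 (weeks 13-28) = 6.1702 before rounding of the parts.
- Example, cut at week 15 with a 2-week lag: weeks 14 and 15 are pending, 0.5488 + 0.4066 = 0.9554, and 1 − 0.9554/6.1702 = 0.845.

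| Lag (weeks) | Cut 3 weeks after peak | 4 weeks | 5 weeks |
|---|---|---|---|
| 0 | 1.000 | 1.000 | 1.000 |
| 1 | 0.934 | 0.951 | 0.964 |
| 2 | 0.845 | 0.885 | 0.915 |
| 3 | 0.725 | 0.796 | 0.849 |
| 4 | 0.563 | 0.676 | 0.760 |

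At the 4-week lag with the earliest cut, the peak week itself is still pending. Adding P × p × g returns 1.000 in every cell. A second assumed season (30 weeks, peak at week 15) gives errors of −6.6%, −15.9%, −28.9% and −47.0% for a cut 3 weeks after the peak, and −3.4%, −8.2%, −14.8% and −24.1% for 5 weeks.

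**Study level.** If Season 3 supplies half of all cases (assumed), the study total is low by half the Season 3 shortfall: 1.8-3.3%, 4.2-7.7%, 7.5-13.7% and 12.0-21.8% at lags 1 to 4. A false trigger then needs the true total to exceed the redacted threshold by less than 1/(1 − shortfall) − 1, at most 3.4%, 8.4%, 15.9% and 28.0%. The calculated Season 4 total would rise by the same percentages if the predicted count were used for the attack rate.

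**Relaxing the assumptions.** On the 30-week season, net errors at lags of 0 to 4 weeks are:

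- Bell-shaped decline, cut at 5 weeks: +14.2%, +9.7%, +3.6%, −3.9%, −12.7%.
- Exponential influenza plus 20 background ILIs per week, cut at 5 weeks: +4.9%, +1.5%, −3.3%, −9.9%, −19.2%.
- Exponential decline, Season 1 positivity 1.3 times that of Season 3, cut at 3 weeks: +4.9%, −1.7%, −11.0%, −24.0%, −42.0%.
- Bell-shaped decline with the same 1.3 ratio, cut at 3 weeks: +47.1% falling to +11.1%, with no change of sign.

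**Confirmed-case route.** The SAP does not say where this forecast starts. If it starts at the data cut, the weeks still pending are lost and the shortfall is the one tabulated. If it starts the week after the last fully resulted week, nothing is lost.

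**Cost of an unneeded interim.** With the power-family spending function (φ = 2) and an assumed 60-80% information, the interim spends 0.025 × t² = 0.009 to 0.016. The final one-sided alpha becomes 0.0208 to 0.0187, and a nominal 90% power becomes 89.1% to 88.9% counting either look.

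**The case against.** The strongest reply is that the practical effect may be small. Turnaround may be short. The section switches to observed cases once results are available, and it allows Season 2 positivity and epidemiological data to be considered. The trigger starts only planning, and SAP 3.1 says an extension may be considered. SAP 5.4.4.1 predicts the Season 3 total again at the interim, and the Executive Board makes the stopping decision (SAP 5.4.4). Final alpha is reduced only if the interim runs and its superiority rule is not met (SAP 5.1.1.2).

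These facts stand, and they keep the point minor. They do not close the gap. The switch to observed cases sets no rule for a part-complete backlog. The optional data concern positivity or the remaining season, not ILIs already reported. The second prediction comes only after the first has decided whether the interim runs.

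Three stronger readings are tempting, and the documents support none of them.

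- A reader might infer that the forecast is always too low. Only the omitted term has a fixed sign; the other parts of the forecast can err upwards by more.
- A reader might infer that laboratory lag alone sets the direction, with one to two weeks harmless and under-prediction only from about three. That pattern comes from assuming a flat non-influenza ILI background. On the 28-week season (12 scenarios), a background centred on week 14 over-predicts in all 12 at a 3-week lag (1.07-1.30), and one centred on week 6 under-predicts in all 12 even with no lag.
- A reader might infer that a pending term is unsafe unless positivity is matched week by week to Season 1. With constant positivity the simple term is exact. Even with a flat background, week-matching shows no real gain over the SAP's steps at lags of 1 and 2 weeks when Season 1 is allowed to differ from Season 3: mean absolute error 0.054 and 0.062, against 0.055 and 0.064.

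**Conclusion.** The point holds as a counting gap: pending Season 3 ILIs are in no step of SAP 5.4.3, and no other section repairs this before the forecast is used. Under the section's own assumptions the forecast is low at every lag above zero, to about 0.93-0.96, 0.85-0.92, 0.73-0.85 and 0.56-0.76 of true Season 3 cases at lags of 1, 2, 3 and 4 weeks. The season shape, cut timing and lags are all assumed. In practice the net error also depends on the shape of the decline, the timing of the cut, and how whole-season Season 1 positivity compares with post-peak positivity in Season 3. It can therefore go either way.

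The consequences are limited to the Season 4 planning trigger, one of the two interim conditions, and possibly the Season 4 attack rate. A reader might fear for Type I error, but the forecast uses pooled blinded counts, so it is unaffected. Severity: minor.

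**What to change.** In SAP 5.4.3:

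- Define a laboratory data cut-off so that each Season 3 ILI is counted exactly once, as resulted, pending or future.
- Apply steps 1 to 3 to pending plus future ILIs, with the same positivity and per-protocol factors, and keep step 4 for resulted cases.
- In the confirmed-case version, start the forecast the week after the last fully resulted week.

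This removes the omission but not any error in the curve or the positivity factor: in the bell-shaped example above (cut at 5 weeks, constant positivity) the corrected forecast stays at +14.2% at every lag. A forecast using positivity from the matching post-peak weeks of Season 1 may be shown as a sensitivity analysis, but it is not required.

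The cost is one definition, a changed step and a few lines of blinded programming. No further data or subjects are needed.
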